7.1. Discontinuation of Study Intervention

With the implementation of Protocol Amendment 3, all participants had to stop JNJ-6379 treatment immediately.

Treatment with JNJ-3989 (and PegIFN- α 2a during Treatment Period 2) must be discontinued before Week24/EOSI if any of the discontinuation criteria listed below are met. Criteria specific for this ISA are highlighted (colored fill). For the few criteria from the Master Protocol that are specified or more restricted in this ISA, the changes compared to the Master Protocol are also highlighted (colored fill). If JNJ-3989 is discontinued, PegIFN- α 2a (only applicable in Treatment Period 2) should also be discontinued. NA treatment may be continued or, in consultation with the sponsor, discontinued based on investigator judgement.

The discontinuation criteria are:

- The participant withdraws consent to receive study intervention.
- The investigator believes that for safety or tolerability reasons (eg, AE) it is in the best interest of the participant to discontinue JNJ-3989 (and PegIFN- α 2a, if applicable).
- The participant becomes pregnant.
- The participant has a \geq grade 3 rash (see Section 10.6, Appendix 6: Rash Management) or allergic reaction (see Section 8.3.6.3, Acute Systemic Allergic Reactions).
- The participant has signs of hepatic decompensation (ie, clinical evidence of ascites, bleeding varices, or hepatic encephalopathy) or an increase in direct bilirubin $>1.5x$ ULN in combination with INR $\geq 1.5x$ ULN or albumin <3.0 g/dL, treatment with JNJ-3989 should be discontinued and alternative treatment options (outside the study) should be considered in discussion with the sponsor.
- The participant has a confirmed \geq grade 3 eGFR abnormality, considered at least possibly related to JNJ-3989 (or PegIFN- α 2a, if applicable) that persists despite change of tenofovir disoproxil to ETV or TAF (if the patient was receiving tenofovir disoproxil). Change of NA treatment should be considered according to the prescribing information (see Section 8.3.6.5, Renal Complications).
- The participant has a QTcF prolongation (defined as a QTcF value of >500 ms, or an increase from baseline of >60 ms) at any given time point.
- The participant requires ≥ 7 days of treatment with any of the disallowed medications listed in Section 6.5, Concomitant Therapy, and does not intend to discontinue treatment with the disallowed medication.
- The participant has confirmed HBV virologic breakthrough (ie, confirmed on-treatment HBV DNA increase by >1 log₁₀ IU/mL from nadir or confirmed on-treatment HBV DNA level >200 IU/mL in participants who had HBV DNA level $<$ LLOQ of the HBV DNA assay).
In case of virologic breakthrough, the same assessments will be done at an unscheduled visit as will be done in case of an ALT flare, but no PBMC sample will be taken (see Section 8.3.6.4, Intervention emergent ALT/AST Elevations, and Schedule of Activities).
- The participant has ALT/AST elevations, as described in Section 8.3.6.4, Intervention-emergent ALT/AST Elevations.

Note: The grades are based on the DAIDS Toxicity Grading Scale (see Section 10.9, Appendix 9: DAIDS Table).

In addition, PegIFN- α 2a must immediately be discontinued for any of the following reasons:

- Participant has platelet count $<25,000$ cells/mm³.
- Participant has ANC <500 cells/mm³.

Note: PegIFN- α 2a treatment can be restarted when ANC values return to more than 1,000 cells/mm³ (see details in Section 6.7, Dose Modification)

- Participant develops evidence of hepatic decompensation during treatment, or ALT increase clinically significant or accompanied by direct bilirubin increase.
- Participant develops thyroid disorders or diabetes during treatment and cannot be controlled with medication.
- Participant develops new or worsening ophthalmologic disorders.
- Participant develops any deterioration of cardiovascular status.
- Participant develops serious, acute hypersensitivity reaction (e.g., urticaria, angioedema, bronchoconstriction, anaphylaxis).
- Participant develops serious infection (bacterial, viral, fungal) and sepsis.
- Participant develops persistent or unexplained pulmonary infiltrates or pulmonary function impairment.
- Participant with onset or worsening of psoriatic lesion.
- Participant develops moderate or severe depression, or other psychiatric symptoms (for mild depression, treatment discontinuation may be considered).

Note: Participants who develop a neuropsychiatric AE during PegIFN- α 2a treatment, will be monitored closely until the neuropsychiatric AE resolves, with frequent (at least weekly) follow-up phone calls.

- Participant develops colitis symptoms (such as but not limited to abdominal pain, bloody diarrhea, and fever).
- Participant develops symptoms or signs suggestive of pancreatitis.

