8.3.6.4. Intervention-emergent ALT/AST Elevations

Elevated liver enzyme activity can be triggered by the underlying HBV disease as well as by the study intervention.

Management of intervention-emergent ALT/AST elevations is presented graphically in Section 10.7, Appendix 7: Intervention-emergent ALT/AST Elevations, and is described below.

Any intervention-emergent elevation of ALT and/or AST $\geq 3x$ ULN and $\geq 3x$ nadir (ie, lowest value during study participation) should trigger an assessment of confounding factors (alcohol intake, change in concomitant medication, and comorbidities) and should trigger a confirmatory study visit to repeat laboratory testing of AFP, ALT, AST, ALP, bilirubin (total and direct), INR, albumin, and HBV DNA. Additional tests should be considered based on clinical judgement (refer to Section 10.7, Appendix 7: Intervention-emergent ALT/AST Elevations). This confirmatory visit should be scheduled as soon as possible within 7 days of the receipt of the initial ALT/AST results. In case the repeat laboratory testing shows an isolated ALT/AST elevation (ie, with stable albumin, bilirubin [total and direct], and INR) the participant may continue study intervention. In case of confirmed ALT elevation $>1,000$ U/L and $\geq 3x$ the baseline value, JNJ-3989 (and PegIFN- α 2a in Treatment Period 2) should be discontinued. In both cases, NA treatment should be continued. The participant will be monitored (laboratory testing of AFP, ALT, AST, ALP, bilirubin [total and direct], INR, albumin, and HBV DNA) on a weekly basis or more frequently until ALT and/or AST levels have returned to $<5x$ ULN and HBV DNA is $<20,000$ IU/mL.

If the ALT and/or AST level is $\geq 3x$ ULN and $\geq 3x$ nadir and is associated with any of the following laboratory results or clinical symptoms:

- INR ≥ 1.5 , OR
- direct bilirubin $>1.5x$ ULN, OR
- serum albumin <3.0 g/dL, OR
- ascites, hepatic encephalopathy, or liver-related symptoms (eg, severe fatigue, nausea, vomiting, right upper quadrant pain in the absence of an alternative medical explanation), OR
- other indication of reduced liver function,

the participant should discontinue JNJ-3989 (and PegIFN- α 2a in Treatment Period 2) and should be monitored on a weekly basis or more frequently, or as per good clinical practice, until ALT and

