AST levels have returned to <5x ULN, HBV DNA is <20,000 IU/mL and, if present, liver-related symptoms have improved. NA treatment should be continued. Additional tests can be considered based on clinical judgement (refer to Section 10.7, Appendix 7: Intervention-emergent ALT/AST Elevations).

PegIFN- α 2a may need to be discontinued in clinically significant cases of ALT increase or in combined increase of ALT and direct bilirubin. Refer to the prescribing information for PegIFN- α 2a ([Pegasys SmPC](#) or [Pegasys USPI](#)).

The NA re-treatment criteria during follow-up are presented in Section 6.7.1, NA Re-treatment Criteria and Monitoring After Stopping of NA.

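### PegIFN-α2a must be stopped at once under Protocol section 7.1, but only may need to be stopped under section 8.3.6.4, for the same ALT and direct bilirubin triggers

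*Protocol*

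**What the plan says.** Protocol section 7.1 has two layers. A general list gives criteria for stopping JNJ-3989 (and PegIFN-α2a in Treatment Period 2); one entry refers to section 8.3.6.4 for ALT/AST elevations. A second list, introduced as additional, applies to PegIFN-α2a alone, which "must immediately be discontinued for any of the following reasons". Its liver entry reads: "Participant develops evidence of hepatic decompensation during treatment, or ALT increase clinically significant or accompanied by direct bilirubin increase". The same list marks discretion where discretion is meant: "for mild depression, treatment discontinuation may be considered".

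Section 8.3.6.4 sets graded rules once ALT and/or AST reaches both 3x ULN and 3x nadir:

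- If repeat testing shows "an isolated ALT/AST elevation (ie, with stable albumin, bilirubin [total and direct], and INR) the participant may continue study intervention".
- Confirmed ALT above 1,000 U/L and at least 3x baseline calls for JNJ-3989 and PegIFN-α2a to be stopped.
- They are also to be stopped when the elevation comes with any one of several signs: INR of at least 1.5, direct bilirubin above 1.5x ULN, albumin below 3.0 g/dL, ascites, encephalopathy or liver-related symptoms, or another indication of reduced liver function.

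A separate closing sentence says PegIFN-α2a "may need to be discontinued in clinically significant cases of ALT increase or in combined increase of ALT and direct bilirubin". It then sends the reader to the prescribing information and does not mention the PegIFN-α2a list in 7.1.

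**The concern.** The drug and the two triggers are the same in both sections, but the required action is not. The triggers are a clinically significant ALT increase, and an ALT increase together with a direct bilirubin increase. This is a liver-safety stop, and the Protocol treats ALT/AST elevation as an event of special interest.

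A site handling an ALT rise is also more likely to meet the weaker wording. The ALT/AST footnote in the Schedule of Activities (section 1.3) refers to Appendix 7, which 8.3.6.4 describes as the graphic form of its own management rules. The general ALT/AST entry in 7.1 points to 8.3.6.4 as well. A site could therefore follow 8.3.6.4 in good faith and keep dosing PegIFN-α2a where 7.1 requires an immediate stop. SAP Appendix 4 has a major-deviation category for participants who met withdrawal criteria but were not withdrawn, so the ambiguity could also affect how such a case is classified.

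**Working it through.** No arithmetic applies. The check is to take the situations that can arise during PegIFN-α2a dosing and read each section's instruction for PegIFN-α2a.

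| Situation | Section 7.1 | Section 8.3.6.4 | Agree? |
|---|---|---|---|
| A. Confirmed ALT >1,000 U/L and ≥3x baseline | Stop (general list, by reference to 8.3.6.4) | Stop | Yes |
| B. ALT and/or AST ≥3x ULN and ≥3x nadir, with any listed sign of reduced liver function | Stop | Stop | Yes |
| C. ALT ≥3x ULN and ≥3x nadir, direct bilirubin increased but ≤1.5x ULN, no other listed sign | Stop immediately (ALT plus bilirubin trigger) | Discretionary | No |
| D. ALT ≥3x ULN and ≥3x nadir, isolated, short of the rule in A, judged clinically significant | Stop immediately (clinical significance trigger) | Study intervention may continue; PegIFN-α2a stop discretionary | No |
| E. ALT increase short of 3x ULN and 3x nadir, direct bilirubin increased but ≤1.5x ULN, no other listed sign | Stop immediately (neither trigger in 7.1 has an ALT floor) | Graded rules not reached; discretionary sentence only | No |

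Row C is the clearest divergence. The permission to continue requires stable total and direct bilirubin, so it is not available. The bilirubin stop requires more than 1.5x ULN, so it is not met. What remains for PegIFN-α2a is the closing sentence with its discretionary verb.

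Row D depends on how study intervention is defined. Appendix 1 includes PegIFN-α2a in Treatment Period 2, so the permission to continue covers it unless something else removes it.

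Three features of 7.1 support reading its entry as mandatory. The introduction to the list says so. The list is additional to the general criteria, so the general reference to 8.3.6.4 does not absorb it. And the mild-depression entry shows that the list states discretion when it intends it.

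Both sections are current text. Neither the Protocol nor the SAP gives an order of precedence between them. The Master Protocol was not available for this check.

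**The case against.** The strongest reply is that 7.1 already governs. It is the discontinuation section, it brings in 8.3.6.4 by reference, and it then adds a stricter list for PegIFN-α2a. On that reading the discretionary sentence permits stopping and forbids nothing, so a site that stops complies with both. This stands, and a reader might otherwise infer that the two instructions cannot both be followed; they can. The difficulty runs one way: a site that continues under 8.3.6.4 can breach 7.1, and nothing in 8.3.6.4 warns it.

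For the first trigger, clinical significance is undefined in both sections, so most of the judgement lies in deciding whether the trigger is met. That makes row D the weaker case. It does not help with row C, where the bilirubin trigger does not depend on that judgement.

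A reader might also infer that 8.3.6.4 stops PegIFN-α2a only once direct bilirubin passes 1.5x ULN. The text does not support this: that threshold, "direct bilirubin $>1.5x$ ULN, OR", is one of several alternatives, and a site could place a rising bilirubin during an ALT flare under other indications of reduced liver function. The divergence therefore holds only when no other listed sign is judged present. Nor can its width be derived from the direct bilirubin limit of 1.2x ULN in section 5.2. That limit is an eligibility criterion, and only exclusion criterion A25 is rechecked before PegIFN-α2a starts at Week 12.

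The Appendix 7 chart and the prescribing information could not be seen, and either may carry the stop. The plan also has a confirmatory visit within 7 days, at least weekly liver testing, and review by the Data Review Committee and the flare panel. These limit the likely harm but leave the two sentences in disagreement.

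**Conclusion.** The inconsistency is real and should be corrected, within limits. For a clinically significant ALT increase, or an ALT increase with a direct bilirubin increase, 7.1 makes the PegIFN-α2a stop mandatory and immediate, while 8.3.6.4 leaves it open. The sections agree in rows A and B and diverge below those rules, most clearly in row C.

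How many participants would fall in that zone is unknown, and the documents give no basis for estimating it. They do not support a claim that participants were harmed or that the primary endpoint is biased. The conclusion rests on reading the 7.1 entry as written, and on the absence of any statement of precedence in the Protocol or SAP. Confidence is high on the difference in wording and its consequence for a site that continues dosing; the practical frequency is not known.

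**What to change.** Four changes to the Protocol:

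1. In the closing PegIFN-α2a sentence of section 8.3.6.4, replace the discretionary verb with *must be discontinued immediately (see the PegIFN criteria in Section 7.1)*.
2. In the same section, make the permission to continue study intervention during an isolated elevation subject, for PegIFN-α2a, to the section 7.1 criteria.
3. In section 6.7, which leaves PegIFN-α2a dose adjustment for laboratory abnormalities to the prescribing information and the investigator's assessment, state that dose adjustment does not replace a mandatory stop under 7.1. The restart provision there can stay as written.
4. Check that the Appendix 7 chart agrees, and correct it if it does not.

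Because 7.1 sets no numeric threshold for either trigger, the sponsor's clinicians may wish to add one when making these edits; the alignment does not depend on it.

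The cost is two amended sentences in 8.3.6.4, one added sentence in 6.7 and a check of one chart. No visits, samples or procedures are added, and no stop is imposed that 7.1 does not already require.

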		W-4 to 0 ^b	D1 ^c	W2	W4	W8	W12	W14	W16	W20	W24 /EOSI /WD ^e	FU W2	FU W4	FU W8	FU W12	FU W16 ^{gg}	FU W20 ^{gg}	FU W24	FU W28 ^{gg}	FU W32 ^{gg}	FU W36	FU W40 ^{gg}	FU W44 ^{gg}	FU W48 /EOS /WD ^e _{aaa}
Visit Day (D)/Week (W)	W-4 to 0 ^b	D1 ^c	W2	W4	W8	W12	W14	W16	W20	W24 /EOSI /WD ^e	FU W2	FU W4	FU W8	FU W12	FU W16 ^{gg}	FU W20 ^{gg}	FU W24	FU W28 ^{gg}	FU W32 ^{gg}	FU W36	FU W40 ^{gg}	FU W44 ^{gg}	FU W48 /EOS /WD ^e _{aaa}	
Study Day (Window)	-28 to 0	1	15 +/-2d	29 +/-2d	57 +/-2d	85 +/-2d	99 +/-3d	113 +/-3d	141 +/-3d	169 +/-3d	15 +/-4d	29 +/-4d	57 +/-4d	85 +/-4d	113 +/-4d	141 +/-4d	169 +/-4d	197 +/-4d	225 +/-4d	253 +/-4d	281 +/-4d	309 +/-4d	337 +/-4d	
Administration of PegIFN-α2a ^{m,tt}						X	X	X	X															
Dispensation of PegIFN-α2a ^{m,tt}						X		X	X															
Provide PegIFN-α2a self-injection tracker ⁿ						X																		
Review PegIFN-α2a self-injection tracker ^o							X	X	X	X														
Study intervention accountability				X	X	X		X	X	X		(X)	(X)	(X)	(X)	(X)	(X)	(X)	(X)	(X)	(X)	(X)	(X)	(X)
Assess NA treatment completion criteria											X ^{uu}													
Continuous assessment of NA re-treatment criteria, as applicable												(X)	(X)	(X)	(X)	(X)	(X)	(X)	(X)	(X)	(X)	(X)	(X)	(X)
Safety Assessments																								
Complete physical examination ^p	X									X														
Symptom-directed physical examination, including body weight		X	X	X	X	X	X	X	X		X	X	X	X	X	X	X	X	X	X	X	X	X	X
Ophthalmic examination (including funduscopy)	X				X ^q					X ^r														
Vital signs ^s	X	X	X	X	X	X	X	X	X	X	X	X	X	X	X	X	X	X	X	X	X	X	X	X
Triplicate 12-lead ECG ^t	X	X		X		X				X		X												
Injection site reactions (for JNJ-3989 and/or PegIFN-α2a)		X	X	X	X	X	X	X	X	X														
Liver ultrasound ^u		(X)								X							X							X
Clinical Laboratory Tests																								
Hematology ^w	X	X	X	X	X	X	X	X	X	X	X	X	X	X	X		X	X		X		X	X	X
Blood chemistry (including liver function tests) ^{v,x,y}	X	X	X	X	X	X	X	X	X	X	X	X	X	X ^{rr}	X ^{rr}	X ^{rr}	X	X ^{rr}	X ^{rr}	X	X	X	X	X
Blood coagulation	X	X		X	X	X	X	X	X	X	X	X		X			X			X		X	X	X
Urinalysis ^z	X	X		X	X	X	X	X	X	X	X ^{ww}	(X)	(X)	(X)	(X)	(X)	(X)	(X)	(X)	(X)	(X)	(X)	(X)	X
Urine chemistry ^{aa}	X	X		X	X	X	X	X	X	X	X ^{ww}	(X)	(X)	(X)	(X)	(X)	(X)	(X)	(X)	(X)	(X)	(X)	(X)	X

Study Period	Screenin g	Treatment Period 1 ^{a,d,e}				Treatment Period 2 ^{a,d,e}					Follow-up ^{a,e,qg}													

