Blood sampling for sparse PK of JNJ-3989 and optionally NA and PegIFN-α2a ⁱⁱ		X ^{jj}		X ^{jj,ll}		X ^{jj}			X ^{jj,ll}																
Blood sampling for intensive PK of JNJ-3989 and optionally NA and PegIFN-α2a (PK substudy) ^{kk}				X					X																
Exploratory Host Biomarkers																									
Whole blood RNA gene expression		X				X	X	X		X														X	
Whole blood single cell profiling		X			X	X				X		X	X	X			X			X				X	
Host serum proteins (eg, cytokines)		X		X	X	X		X	X	X		X	X	X			X			X				X	
Antidrug antibodies (to JNJ-3989 and optionally PegIFN-α2a)		X			X			X		X				X			X							X	
Immune Monitoring																									
Immune cells (PBMCs) (selected sites only) ^{mm}		X				X				X		X		X			X							X	
Pharmacogenomics (DNA)																									
HLA typing		X																							
Exploratory host genotyping (optional) ⁿⁿ		X																							
Epigenetic research (optional) ⁿⁿ		X				X				X		X		X			X							X	
Ongoing Participant Review																									
Concomitant therapy ^{oo}		X	X	X	X	X	X	X	X	X	X	X	X	X	X	X	X	X	X	X	X	X	X	X	X
Adverse events ^{oo, xx}		X	X	X	X	X	X	X	X	X	X	X	X	X	X	X	X	X	X	X	X	X	X	X	X

General Note: The ECGs should be completed before any tests, procedures or other consultations for that visit.

For Japan only, twice weekly visits are to be scheduled during the first week of treatment with PegIFN-α2a (ie, Week 12), followed by weekly visits up to Week 23, for assessment of safety (injection site reactions, physical examination, ophthalmic examination [when indicated], vital signs), hematology (only up to Week 20), concomitant

therapy and adverse events. During Week 12 (first 2 visits with PegIFN- α 2a), the study day visit window is +/-2d. After Week 12, the study day visit window is +/-3d until Week 24.

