- j. Participants must have absence of signs of cirrhosis or portal hypertension (absence of nodules, smooth liver contour, normal portal vein, spleen size <12 cm) and absence of signs of HCC or clinically relevant renal abnormalities on an abdominal ultrasound performed within 3 months prior to screening or at the time of screening. In case of suspicious findings on conventional ultrasound the participant may still be eligible if HCC or clinically relevant renal abnormalities have been ruled out by a more specific imaging procedure (contrast-enhanced ultrasound, CT or MRI).
- k. HBV genotype will be determined at baseline using a standard genotyping assay if HBV DNA levels are sufficiently high. Available historical data on a previous HBV genotype assessment will also be collected in the CRF. Exploratory genotyping may be performed.
- l. Not applicable for the WD visit.
- m. In between study visits, participants will take NA at home and will bring their NA with them to each study visit. At study visits, NA should be taken on site. Weekly PegIFN- α 2a administration should preferably be done on the same day of the week in the evening by self-injection. A total of 12 injections should be administered, starting at Week 12, with the last injection during Week 23. If desired, participants can also choose to have the weekly administration of PegIFN- α 2a performed on site irrespective of the time of day. For participants in Japan, weekly administration of PegIFN- α 2a must be performed at the study site by the investigator or his/her designee.
- n. Only applicable in case of self-injection.

- o. Participants who are administering PegIFN- α 2a by self-injection will be requested to complete a self-injection tracker. Refer to Section 6.4, Study Intervention Compliance, for more details.
- p. Complete physical examination, including height (only at screening), body weight, skin examination, and other body systems.
- q. For participants with a risk factor (eg, diabetes or hypertension), an ophthalmic examination should be repeated at Week 8 (+/- 3 weeks) at the investigator's discretion in case their condition changes. Any participant experiencing a decrease or loss of vision at any time point during study participation, must have a prompt ophthalmic examination. Medical records of the examination should be collected and assessed by the investigator.
- r. A +/- 3-week visit window is allowed for the ophthalmic examination at Week 24.

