A18 Female participants who are pregnant, or breast-feeding, or planning to become pregnant while enrolled in this study or within 90 days after the last dose of study intervention.
(adapted from M18)

A19 Male participants who plan to father a child while enrolled in this study or within 90 days after the last dose of study intervention.
(adapted from M19)

M20 Participants who had major surgery (eg, requiring general anesthesia), excluding diagnostic surgery, within 12 weeks before screening; or will not have fully recovered from surgery; or have surgery planned during the time of expected participation in the study.

Note: Participants with planned surgical procedures to be conducted under local anesthesia may participate.

M21 Participant is an employee of the investigator or study site, with direct involvement in the proposed study or other studies under the direction of that investigator or study site, as well as family members of the employees or the investigator.

M22 Vulnerable participants (eg, incarcerated individuals, individuals under a legal protection measure).

A23 Criterion modified per Amendment 3

A23.1 Participants with known allergies, hypersensitivity, or intolerance to JNJ-3989 or its excipients (refer to the IB [IB JNJ-3989 2020]) and NA and PegIFN- α 2a or their excipients (refer to the respective prescribing information).

A24 Participants with prior IFN use.

A25 A25.1 Criterion modified per Amendment 1

Criterion modified per Amendment 3

A25.2 Participants who meet any of the additional exclusion criteria for PegIFN- α 2a as described in the prescribing information (refer to [Pegasys SmPC](#) or [Pegasys USPI](#) for a complete list) per the investigator's discretion. Key exclusion criteria for PegIFN- α 2a include:

1. Patients with signs or symptoms compatible with autoimmune disorders.
2. Participants with bone marrow suppression.
3. Patients with hypoglycaemia, hyperglycaemia, and/or diabetes mellitus, who cannot be effectively controlled by medication.
4. Participants with pre-existing ophthalmologic disorders.
5. Participants with one or more of the following laboratory abnormalities:
 - Absolute neutrophil count $<1,500$ cells/mm³ ($<1,000$ cells/mm³ for black or African American participants).
 - Serum creatinine >1.5 x ULN.
 - Inadequately controlled thyroid function (thyroid stimulating hormone [TSH] and thyroxine [T4]).
 - CD4+ cell count <200 cells/mm³.

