10.2. Appendix 2: Clinical Laboratory Tests

The clinical laboratory tests will be performed by the selected laboratory according to the [Schedule of Activities](#). The tests to be performed are discussed in Section 8.2.4 of the Master Protocol PLATFORMPAHPB2001.

Below is the list of protocol-required safety laboratory assessments that will be evaluated in this study. The additional assessments specific for this ISA are highlighted (colored fill).

Protocol-required Safety Laboratory Assessments

Laboratory Assessments	Parameters		
Hematology	Platelet count Red blood cell count Hemoglobin Hematocrit	RBC Indices: MCV MCH % Reticulocytes	White Blood Cell (WBC) count with Differential: Neutrophils Lymphocytes Monocytes Eosinophils Basophils
	Note: A WBC evaluation may include any abnormal cells, which will then be reported by the laboratory. An RBC evaluation may include abnormalities in the RBC count, RBC parameters, or RBC morphology, which will then be reported by the laboratory. In addition, any other abnormal cells in a blood smear will also be reported.		
Clinical Chemistry	Sodium Potassium Chloride Bicarbonate Blood urea nitrogen (BUN) Creatinine Glucose Aspartate aminotransferase (AST) Alanine aminotransferase (ALT) Gamma-glutamyltransferase (GGT) α_1 -acid glycoprotein Calculated creatinine clearance (by CKD-EPI formula) Fibrinogen (on blood) eGFR calculation based on Cystatin C	Total, direct, indirect bilirubin Alkaline phosphatase Creatine phosphokinase (CPK) Lactic acid dehydrogenase (LDH) Uric acid Calcium Phosphate Albumin Total protein Total cholesterol High-density lipoprotein cholesterol Low-density lipoprotein cholesterol Triglycerides Magnesium Lipase Amylase (reflex testing of pancreatic amylase should be done in case of amylase or lipase increase from screening onwards)	

Laboratory Assessments	Parameters	
Routine Urinalysis	Dipstick Specific gravity pH Glucose Protein Blood Ketones Bilirubin Urobilinogen Nitrite Leukocyte esterase	Sediment (if dipstick result is abnormal) Red blood cells White blood cells Epithelial cells Crystals Casts Bacteria
Urine Chemistry (quantitative measurement)	Creatinine Sodium Phosphate	Glucose Protein Albumin
Renal Biomarkers	Retinol binding protein ^a Beta-2-microglobulin ^a Note: Other biomarkers might be measured.	

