Other Tests	
 • At screening, a follicle-stimulating hormone (FSH) test will be performed for postmenopausal women (see Section 10.5, Appendix 5). • At screening, a HIV-1 and -2 test, and hepatitis A, C, D, and E tests will be performed. • At screening, hemoglobin A1c will be measured. • At screening and time points as indicated in the Schedule of Activities, alpha-fetoprotein will be measured. • At screening and time points as indicated in the Schedule of Activities, tests for coagulation parameters will be performed. The international normalized ratio (INR) will be calculated by the central laboratory. • At screening serum pregnancy testing will be done for women of childbearing potential only. • At baseline (Day 1) and time points as indicated in the Schedule of Activities, a urine pregnancy test will be performed for women of childbearing potential only. • Testing for HBsAg, HBeAg, and anti-HBs, anti-HBc and anti-HBe antibodies at the time points indicated in the Schedule of Activities. • Thyroid function tests (TSH and T4) will be performed at screening and time points indicated in the Schedule of Activities. • Optional tests in response to ALT flare (refer to Section 10.7, Appendix 7): 
 ○ Testing for HIV-1 and -2, and hepatitis A, C, and E ○ Testing for CMV, HSV, EBV infection ○ Ig-Electrophoresis 	

^a Retinol binding protein and beta-2-microglobulin need to be assessed based on the same urine sample.

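### No thyroid test is scheduled while participants receive PegIFN-α2a, although the protocol requires stopping PegIFN-α2a for an uncontrolled thyroid disorder that develops on treatment

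*Protocol*

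**What the plan says.** Protocol Section 7.1 lists reasons for which PegIFN-α2a must be stopped at once. One reads: "Participant develops thyroid disorders or diabetes during treatment and cannot be controlled with medication".

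The dosing window is in footnote m of the Schedule of Activities (Section 1.3): "A total of 12 injections should be administered, starting at Week 12, with the last injection during Week 23".

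The TSH and T4 row of that schedule has two marks, Screening and Week 8. Appendix 2 (Section 10.2) sets no further time points and points back to the schedule: "Thyroid function tests (TSH and T4) will be performed at screening and time points indicated in the" Schedule of Activities.

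Exclusion criterion A25 (Section 5.2) shows which measure the protocol itself uses for thyroid control: "Inadequately controlled thyroid function (thyroid stimulating hormone [TSH] and thyroxine [T4". A25 is checked at screening and again before Treatment Period 2.

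SAP Section 5.6.3.1, Table 7, lists TSH and T4 among the laboratory parameters. The text there provides for summaries of each laboratory parameter at each scheduled time point, by analysis phase.

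**The concern.** The stopping criterion concerns disorders that arise during treatment, but both scheduled thyroid tests come before PegIFN-α2a starts. They can inform eligibility, not on-treatment monitoring.

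An asymptomatic Grade 1 thyroid change, which the DAIDS table defines by an abnormal laboratory value without symptoms, does not itself trigger Section 7.1. It can, however, be found and treated late, and nobody can judge whether a disorder is controllable with medication until it has been found. Once a disorder is diagnosed, repeat TSH and T4 would be expected as follow-up of that event, so the gap is in first detection.

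There is also a reporting consequence. Laboratory abnormalities throughout the study are part of the secondary safety endpoint. The only scheduled post-baseline thyroid value is at Week 8, in Treatment Period 1, so by-visit summaries will have no scheduled thyroid data for Treatment Period 2 or follow-up. Unscheduled results enter the worst-case tables, but only for participants someone chose to test.

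**Working it through.** **1. Which columns carry the TSH/T4 marks.** Counting fields against the 23 visit columns puts the marks in field 1 (Screening) and field 5. Two other rows fix field 5 as Week 8:
- The ophthalmic row has its second mark in the same field, and footnote q dates it: "an ophthalmic examination should be repeated at Week 8 (+/- 3 weeks").
- The PegIFN-α2a eligibility row has its second mark one field later, and footnote pp ties that mark to the recheck before Treatment Period 2 (Week 12).

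**2. The PegIFN-α2a window.** Weekly injections from Week 12 to Week 23: 23 − 12 + 1 = 12. This reproduces the protocol's own count of 12.

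**3. Scheduled visits inside the window.** Between the first dose (Week 12) and the last (Week 23), the main schedule has Weeks 14, 16 and 20.

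| Test | Week 14 | Week 16 | Week 20 | Total |
|---|---|---|---|---|
| TSH/T4 | no | no | no | 0 of 3 |
| Glucose (blood chemistry) | yes | yes | yes | 3 of 3 |

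The glucose line rests on the schedule row "Blood chemistry (including liver function tests"), marked at all three visits, and on the Appendix 2 chemistry panel, which includes "Blood urea nitrogen (BUN) Creatinine Glucose Aspartate aminotransferase (AST"). Week 12, Week 24/EOSI and every follow-up visit also lack a TSH/T4 mark.

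**4. Extra visits in Japan.** The additional PegIFN-α2a visits there are "for assessment of safety (injection site reactions, physical examination, ophthalmic examination [when indicated], vital signs), hematology (only up to Week 20"), plus concomitant therapy and adverse events. No thyroid test is listed.

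**5. Gaps from the last scheduled thyroid test (Week 8, Day 57).**
- To the first PegIFN-α2a dose (Week 12, Day 85): 85 − 57 = 28 days, or 4 weeks.
- To the nominal last dose (Week 23, Day 23 × 7 + 1 = 162): 162 − 57 = 105 days, or 15 weeks.
- To Week 24 (Day 169): 169 − 57 = 112 days, or 16 weeks.

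**6. What one on-treatment test would change.**

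| Added test | Gap to last dose | Injections given before that visit's dose | Injections left |
|---|---|---|---|
| Week 16 | 23 − 16 = 7 weeks | 4 | 12 − 4 = 8 |
| Week 20 | 23 − 20 = 3 weeks | 8 | 12 − 8 = 4 |

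**The case against.** The strongest reply accepts the table reading and disputes its weight.

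- **The criterion is clinical and has two parts.** A disorder must develop and then prove uncontrollable with medication. A single test at Week 16 or 20 could only begin that sequence, with few injections left, and nothing shows it would change a stopping decision. This stands as a limit on the size of the consequence. It does not supply a way to find an asymptomatic disorder.
- **Other criteria in the same list also lack a dedicated test at these visits.** No ophthalmic examination or ECG is scheduled at Weeks 14, 16 or 20, and HbA1c is measured only at screening. That is correct, so glucose should not be read as proof that the protocol pairs every criterion with a test. Thyroid still stands out because the protocol names a simple blood measure for it in A25 and blood is already drawn at each visit.
- **The prescribing information may call for thyroid tests.** Section 6.1 tells investigators to follow it, and its content is not in these documents. Clinical practice may therefore be better than the schedule suggests. A general pointer still sets no common time point in this protocol and does not assure uniform data.
- **Other cover exists.** M11 names thyroid disease among illnesses that may exclude, and the Week 8 result can inform the A25 recheck. Adverse events, vital signs and a symptom-directed examination are covered at each visit, and unscheduled visits are allowed for any reason. These reduce the risk, but none is a scheduled test during PegIFN-α2a.
- **The 15-week figure includes 4 weeks before any PegIFN-α2a.** True: the interval from first to last dose is 23 − 12 = 11 weeks, and no scheduled test falls within it.
- **The SAP consequence is modest.** Thyroid is not an adverse event of special interest. One sentence in SAP Section 5.6.3.1 names only the chemistry, hematology, urinalysis and renal biomarker panels, although Table 7 lists TSH and T4 and other sentences cover each laboratory parameter. Thyroid adverse events would be reported in any case.

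**Conclusion.** The concern holds. The protocol schedules no thyroid test during PegIFN-α2a: 0 of 3 visits between the first and last doses, with the last scheduled test 4 weeks before the first dose and about 15 weeks before the last. The consequences are possible late detection and the absence of scheduled thyroid data in Treatment Period 2 and follow-up.

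The conclusion rests on the extracted schedule table, whose Week 8 column is confirmed by two other rows, and is limited to what the protocol schedules. It does not claim that no participant will be tested. The documents give no thyroid incidence on PegIFN-α2a, so the number affected cannot be estimated. The primary endpoint and its analysis are untouched. This is a change that should be made because it is inexpensive; it does not threaten the study's main conclusion.

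**What to change.** Amend the Schedule of Activities in two places:

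- Add TSH and T4 at Week 16 or Week 20, to support the Section 7.1 criterion. Week 16 leaves more doses on which to act; Week 20 reflects more exposure.
- Add TSH and T4 at Week 24/EOSI/WD, to describe thyroid safety at the end of PegIFN-α2a. This test comes after the last planned dose and serves safety characterisation only.

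One follow-up test, for example at FU Week 24, is optional.

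**Cost for 50 participants**, assuming 3 to 5 mL per draw (the documents give no volume for this assay) against the planned 945 mL per participant:

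| Option | Assays | Blood per participant | Share of 945 mL |
|---|---|---|---|
| Two tests | 2 × 50 = 100 | 6 to 10 mL | 6/945 = 0.6% to 10/945 = 1.1% |
| With follow-up test | 3 × 50 = 150 | 9 to 15 mL | 9/945 = 1.0% to 15/945 = 1.6% |

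The tests use existing blood draws, so no visits, staff or procedures are added. The downside is that some incidental abnormal results will need work-up. If PegIFN-α2a dosing is already complete, the clinical study report should state that no scheduled on-treatment thyroid data exist.
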